7.15 TRIAL REPORTING PERIOD OF SERIOUS ADVERSE EVENTS AND AESIS

The reporting period for SAEs (without regard to causality or relationship) and AESIs is comprised of the period following the signing of the ICF through Week 88. Each AE will be assessed to determine whether it meets seriousness criteria. If the AE is considered serious, the Investigator will complete the SAE/AESI Report form and report the event to the Sponsor within 24 hours of becoming aware of the event. The Investigator may also directly report this event to the IRB/EC according to its standard operating procedures. Expectedness of SAEs will be determined by the Sponsor using reference safety information specified in the Investigator's Brochure and protocol.

An event may qualify for expedited reporting to regulatory authorities if it is an SAE, unexpected per reference safety information and considered related following the guidelines in Section 7.5 (UADE) in line with relevant legislation. All investigators will receive a safety letter notifying them of relevant SUSAR reports. The Investigator should notify the IRB/EC as soon as is practical, of serious events in writing where this is required by local regulatory authorities, and in accordance with the local institutional policy.

At any time after completion of the SAE reporting period, if an investigator becomes aware of an SAE that is suspected by the Investigator to be related to the study drug, the event will be reported to the Sponsor or its designee. If the Investigator becomes aware of an SAE in a study subject after the last scheduled follow-up visit, and considers the event related to prior Study Treatment, the Investigator will report it to the Sponsor or the appropriate designee.

SPONSOR CONTACT INFORMATION

MEDICAL MONITOR: [REDACTED], M.D., Ph. D.
EMAIL: [REDACTED]

SAE REPORTING INFORMATION

EMAIL: [contact]
SAFETY FAX: [REDACTED]
SAFETY PHONE: [REDACTED]

The preferred method for providing SAE forms or SAE supporting documents to the Sponsor or designee is an attachment to an e-mail message, to the email address as indicated above. Any SAE supporting documents provided by facsimile (Fax) are to include a coversheet that identifies the reporter name and contact information of the study site.

All supporting documents for SAE reports, including medical records and diagnostic test results, will include reference to the study subject number. The study site will redact all other patient identifying information present on SAE supporting documents prior to sending the report to the Sponsor.

In addition to providing the SAE report to the Sponsor or designee within 24 hours of becoming aware of the event, the AE that is serious must be recorded in the AEs eCRF. The entry into the eCRF is required to be done as soon as possible.

The Investigator will supply the Sponsor and the IRB/EC with more information as it becomes available and any additional requested information. The original SAE form must be kept at the study site. The Sponsor or its representative will be responsible for determining and in turn, reporting SAEs to regulatory authorities according to the applicable regulatory requirements.

When recording the SAE form, correct medical terminology/concepts are to be used and the use of abbreviations and colloquialisms are to be avoided.

Serious Adverse Events must be followed by the Investigator until resolution, even if this extends beyond the study-reporting period. Resolution of an SAE is defined as the return to baseline status or stabilization of the condition with the expectation that it will remain chronic.

In the event of death, if an autopsy is performed, a copy of the report will be sent to the Sponsor.

In the event of a pregnancy, the Investigator will submit a Pregnancy Form to the Sponsor or designee to the safety email address or fax number within 24 hours of learning of the pregnancy.

7.16 NOTIFICATIONS OF SERIOUS ADVERSE EVENTS

In accordance with local regulations, the Sponsor shall notify the appropriate regulatory authorities, and all participating Investigators in a written safety report of any adverse experience associated with the use of the product that is both serious and unexpected and any significant new safety information that might materially influence the benefit-risk assessment of a medicinal product, sufficient to consider changes in product administration or overall conduct of a clinical investigation. The Sponsor will notify regulatory agencies within the time frame specified by local requirements but no later than 10 working days for UADE, 7 days for a fatal or life-threatening SUSAR and 15 days for all other SUSARS (see Section 7.4 and 7.16).

7.17 REPORTING OF CELLECTRA™ 5PSP DEVICE RELATED COMPLAINTS OR DEFICIENCIES

A product complaint (or device deficiency) involves any written, electronic, or oral communication that alleges deficiencies related to the identity, quality, durability, reliability, safety, effectiveness, or performance of a device such as malfunction, misuse or use error and inadequate labeling. A malfunction is defined as the failure of a device to meet its performance specifications or otherwise perform as intended. The intended performance of a device refers to the intended use for which the device is labeled. All product complaints that meet this definition must be reported to the sponsor within 10 days of discovery. Any product complaint that involves an AE or SAE must be also be reported within 24 hours of becoming aware of the event per Sections 7.2 and 7.3.

Any problems experienced including potential malfunctions of the device, error messages displayed on the device screen following treatment or errors that occur during the treatment procedure must be reported to the Sponsor or designee immediately for evaluation. The error reporting or complaint form provided must be completed and emailed to the Sponsor at [contact].

Additional instructions on complaint reporting to be provided separately.

7.18 TRIAL DISCONTINUATION

Inovio Pharmaceuticals Inc. reserves the right to discontinue the trial at this site or at multiple sites for safety or administrative reasons at any time. In particular, a site that does not recruit at a reasonable rate may be discontinued. Additionally, the trial may be discontinued at any time by an IRB, INOVIO, the FDA or other government agencies as part of their duties to ensure that research subjects are protected.

Should the trial be terminated and/or the site closed for any reason, all investigational drugs & devices must be returned to INOVIO or its representative. The PI should ensure their site file documents are complete prior to archiving, and provide copies of any requested documents to INOVIO for its Trial Master File (TMF).

8.0 STATISTICAL CONSIDERATIONS

8.1 STATISTICAL AND ANALYTICAL PLAN

The formal Statistical Analysis Plan is contained in the sections that follow.

8.2 GENERAL CONSIDERATIONS

The statistical analysis of the data will be performed by INOVIO or its representative.

This is a single-arm, multi-center, open-label clinical trial of VGX-3100 in subjects with a diagnosis of AIN2, AIN3, PAIN2, or PAIN3 associated with HPV types 16 and/or 18. The study's primary endpoint is binary: regression of AIN/PAIN HSIL and viral clearance of HPV-16/18 based on tissue collected at Week 36. The primary hypothesis is that the treatment will result in regression of HSIL and clearance. Secondary efficacy analyses pertain to regression, clearance of HPV-16/18 infection, complete regression, non-progression, and anatomic extent. Other secondary analyses concern safety and cellular immunological measures. Exploratory efficacy analyses concern extended dosing with respect to regression, clearance, clearance among non-anal anatomic locations, and association of miRNA profile, anoscopy, cytology, and virology with efficacy. Other exploratory analyses pertain to humoral and cellular immunological measures, tissue immunological measures, and PRO.

8.3 STATISTICAL HYPOTHESES

The true treatment effect on the primary endpoint is p , where p denotes the true population probability of the primary endpoint. The primary hypothesis of superiority is: $H_0: p \leq 0.15$ vs. $H_1: p > 0.15$. There are no other formal hypotheses.

8.4 ANALYTICAL POPULATIONS

Analysis populations are:

- The modified intention to treat (mITT) population includes all subjects who receive at least one dose of Study Treatment. Analysis of the mITT population will be primary for the analysis of efficacy in this study.
- The per-protocol (PP) population comprises subjects who receive all doses of Study Treatment and have no protocol violations. Analyses on the PP population will be considered supportive of the corresponding mITT population for the analysis of efficacy. Subjects excluded from the PP population will be identified and documented prior to locking of the study database.
- The safety analysis set includes all subjects who receive at least one dose of Study Treatment.

8.5 DESCRIPTION OF STATISTICAL METHODS

8.5.1 PRIMARY ANALYSES

The true treatment effect on the primary endpoint is p , where p denotes the true population probability of the primary endpoint. The primary hypothesis of superiority is: $H_0: p \leq 0.15$ vs. $H_1: p > 0.15$.

A p-value for this hypothesis test and corresponding 95% confidence interval will be computed based on the exact method of Clopper-Pearson. Superiority will be concluded if the one-sided p-value is <0.05 and the corresponding lower bound of the one-sided 95% CI exceeds 0.15.

For the analysis, the efficacy time frame is defined by any time starting from 14 days prior to the specified visit week.

The endpoint will be analyzed in two ways: a) based on all lesions and b) based on qualifying and new lesions.

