Pre-biopsy High Resolution Anoscopy Finding	Minimally required procedure
No lesion	Punch biopsy and photography; biopsy should be collected from within the approximate original boundaries of the study entry HSIL as proximal as possible to the original biopsy site which was previously determined to be HSIL by the PAC. New lesions or lesions that did not qualify at baseline should be biopsied at evaluation.
Single lesion (which was also present at baseline)	Punch biopsy and photography; biopsy should be collected within the boundaries of the original lesion and from the area most suspicious for advanced disease within the lesion by clinical exam. New lesions or lesions that did not qualify at baseline should be biopsied at evaluation.
Multiple lesions	Punch biopsies and photography; biopsy should be collected from the same lesions diagnosed as HSIL from study entry and from the area most suspicious for advanced disease within the lesion by clinical exam. New lesions or lesions that did not qualify at baseline should be biopsied at evaluation.

If HSIL is diagnosed in any Week 36 biopsy, but there is a reduction in the number of intra-anal and/or peri-anal lesion(s), reduction in peri-anal lesion(s) size or no change in peri-anal lesion(s) size from baseline (defined by Subgroup C), the Investigator has the option to administer a 4th dose of VGX-3100 at Week 40, and the subject will continue on the study to have HRA and biopsy at Week 64 of all lesions (qualifying and any other visible), i.e. the second efficacy checkpoint. Alternatively, the Investigator may instead choose to treat the subject with standard of care treatment (i.e. electrocautery, ablation, surgical excision), and the subject will continue on the study without further biopsy unless it is part of standard of care.

In the event of worsening anal or anal/peri-anal HSIL at any time during the trial (defined as any increase in lesion(s) area from baseline or worsening of anal or anal/peri-anal HSIL to cancer), the subject may receive standard of care treatment (i.e. electrocautery, ablation, surgical excision) per the Investigator's judgment but will continue on the study through Week 88 with HRA, but without further biopsy unless it is part of the standard of care.

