3.1 PRIMARY OBJECTIVE(S)

Determine the efficacy of 3 doses of VGX-3100 with respect to combined histopathologic regression of anal or anal/peri-anal HSIL and virologic clearance of HPV-16/18

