3.2 PRIMARY ENDPOINT(S)

Proportion of subjects with no histologic evidence of anal or anal/peri-anal HSIL on histology (i.e., collected via biopsy or excisional treatment) and no evidence of HPV-16/18 at Week 36 from intra-anal and/or peri-anal lesion tissue

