8.5.2 SECONDARY ANALYSES

The secondary efficacy binary endpoints will be analyzed in the same manner as the primary hypothesis, but without the hypothesis test p-values. The efficacy time frame is defined in the same manner as for the primary endpoint. All of the efficacy binary endpoints will be analyzed in two ways: a) based on all lesions and b) based on qualifying and new lesions.

The anatomic extent endpoint will be analyzed by calculating the mean percent change in surface area and the mean percent change in number of lesions and associated 95% t-distribution based confidence intervals.

Post-baseline increases in Flow responses will be summarized with medians and 95% CIs. Valid samples for statistical analysis purposes will be those collected within 14 days of the specified visits. Baseline is defined as the last measurement prior to the first treatment administration.

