8.5.9 EXPLORATORY ANALYSES

The exploratory efficacy binary endpoints will be analyzed in the same manner as the primary hypothesis, but without the hypothesis test p-values. The efficacy time frame is defined in the same manner as for the primary endpoint. All of the efficacy binary endpoints will be analyzed in two ways: a) based on all lesions and b) based on qualifying and new lesions. Also, the Week 64/88 binary endpoints will be analyzed a) overall and b) according to three or four doses received.

Other analyses will examine the relationship between the primary efficacy endpoint and a) miRNA results, b) HRA results, c) cytology results, and d) HPV results. Relationships will be examined with contingency tables and/or logistic regression models which model the primary endpoint versus these results as regressor variables.

Post-baseline ELISA titers will be summarized with geometric means and associated t-distribution based 95% CIs. Post-baseline increases in ELISPOT will be summarized with medians and 95% CIs.

The change in tissue immune response magnitude will be summarized with means and associated t-distribution based 95% CIs.

Patient reported outcomes will be summarized with medians or proportions of subjects with endpoints and associated non-parametric or Clopper-Pearson 95% CIs, for continuous responses and binary responses, respectively.

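### The Week 36 efficacy time frame has a start and no end, so Week 64 tissue and late non-study treatment fall inside the primary endpoint as written

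*Protocol*

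**What the plan says.** All references are to protocol Version 3.0. Section 8.1 says that the sections following it are the formal statistical analysis plan, so the rule below is the operative one.

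- **Time frame, Section 8.5.1:** "For the analysis, the efficacy time frame is defined by any time starting from 14 days prior to the specified visit week". No closing bound follows.
- **Reuse:** Sections 8.5.2 and 8.5.9 carry the rule to the secondary and exploratory binary endpoints: "The efficacy time frame is defined in the same manner as for the primary endpoint".
- **Objective, Section 3.1:** "Determine the efficacy of 3 doses of VGX-3100 with respect to combined histopathologic regression".
- **Endpoint, Section 3.2:** "no evidence of HPV-16/18 at Week 36 from intra-anal and/or peri-anal lesion tissue". Section 8.2 describes it as "regression of AIN/PAIN HSIL and viral clearance of HPV-16/18 based on tissue collected at Week 36".
- **Later tissue, synopsis, Study Design:** where HSIL is found at Week 36 in a partial responder (Subgroup C), "the Investigator has the option to administer a 4th dose of VGX-3100 at Week 40", with a further biopsy at Week 64. Subjects without HSIL at Week 36 are also biopsied again at Week 64.
- **Week 64 endpoints:** these are separate and exploratory (Section 3.6).
- **Responder definition, synopsis Table 2:** HSIL or worse, or a positive HPV-16/18 PCR, or any curative non-study treatment makes a non-responder. None of these carries a date limit.
- **Unscheduled biopsies, Section 7.1:** a subject who has one is a non-responder in the efficacy analyses, also without a date limit.
- **Contrast, Section 8.5.2, immunology:** "Valid samples for statistical analysis purposes will be those collected within 14 days of the specified visits". The protocol does close a window elsewhere.

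**The concern.** The only formal hypothesis test in the trial compares the Week 36 response proportion with 15%. The rule that decides which data belong to Week 36 admits everything from Week 34 to the end of follow-up. The Week 36 frame therefore contains the Week 64 frame, and several tissue results per subject inside one frame are built into the design. The protocol does not say which one decides.

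The treatment condition has the same gap. Subjects with HSIL at Week 64 go to standard of care, so a subject who was clear at Week 36 and is treated after Week 64 could be reclassified as a Week 36 non-responder.

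The result may then be neither a Week 36 rate nor a three-dose rate. In an open-label single-arm trial, the choice that settles it could be made with the results in view.

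**Working it through.** **1. Calendar.** Day = 7 × week.

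| Item | Days |
|---|---|
| Week 36 frame opens (252 − 14) | 238 |
| Week 36 visit, ± 1 week | 245–259 |
| Week 40 visit, ± 1 week | 273–287 |
| Week 64 visit, ± 2 weeks | 434–462 |
| Week 88 visit, ± 2 weeks | 602–630 |

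With no upper limit, days 434–462 lie inside the Week 36 frame. A two-sided 14-day bound would run from day 238 to day 266 and end before the Week 40 visit can occur. The ± 1 week at Week 36 governs visit scheduling, not analysis.

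**2. The plan's own power figure.** Inputs are in Sections 8.5.1 and 8.6: one-sided exact test at 0.05, null rate 0.15, alternative 0.40, 24 subjects, 90% evaluable, about 80% power. The rule is the smallest r with P(X ≥ r | n, 0.15) < 0.05.

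| n | r | Actual size | Power at 0.40 |
|---|---|---|---|
| 24 | 8 | 0.020 | 0.808 |
| 22 | 7 | 0.037 | 0.842 |
| 21 | 7 | 0.029 | 0.800 |

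With the evaluable number taken as Bin(24, 0.9), power is 0.815. The stated figure reproduces, and closing the frame does not change it.

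**3. Reading A: a later clear result overrides an earlier positive one.** True Week 36 rate 0.15; a share q of Week 36 non-responders is later counted as clear. Apparent rate = 0.15 + 0.85q, and the false-positive rate is P(X ≥ 8 | 24, apparent rate).

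| q (assumed) | Apparent rate | False-positive rate |
|---|---|---|
| 0 | 0.150 | 0.020 |
| 0.05 | 0.1925 | 0.074 |
| 0.10 | 0.235 | 0.183 |
| 0.20 | 0.320 | 0.521 |

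**4. Reading B: any HSIL or HPV-16/18 in the frame is a non-response.** This is how Table 2 reads. True Week 36 rate 0.40; a share s of Week 36 responders recurs by Week 64. Apparent rate = 0.40 × (1 − s).

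| s (assumed) | Apparent rate | Power, n = 24 |
|---|---|---|
| 0 | 0.40 | 0.808 |
| 0.10 | 0.36 | 0.680 |
| 0.20 | 0.32 | 0.521 |
| 0.30 | 0.28 | 0.351 |

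**5. Reading C: Week 64 tissue is used only where Week 36 tissue is missing.** Assume 10% lack Week 36 tissue (Section 8.6 expects 90% evaluable), all of them are biopsied at Week 64, and a share g is clear. With a true rate of 0.15, the apparent rate = 0.9 × 0.15 + 0.1g.

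| g (assumed) | Apparent rate | False-positive rate |
|---|---|---|
| 0.15 | 0.150 | 0.020 |
| 0.35 | 0.170 | 0.039 |
| 0.50 | 0.185 | 0.061 |

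The documents give no conversion, clearance or recurrence rate at Week 64, so q, s and g are illustrations.

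**The case against.** The strongest reply is that the endpoint text already fixes the time point. Sections 3.2 and 8.2 tie the primary endpoint to Week 36 tissue, and Week 64 tissue has its own endpoints, analysed by three or four doses received. On that view the open end is a loosely worded tolerance for late Week 36 biopsies. This stands as evidence of intent. It does not remove the contradiction with Section 8.5.1, which gives no such purpose.

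A reader might infer that fourth-dose responses will be pooled into the primary endpoint and that the test is therefore anti-conservative. The documents do not support that. A Subgroup C subject already has HSIL in Week 36 tissue, and under Table 2 that alone makes a non-responder. Clear Week 64 tissue changes the classification only if a later result overrides, and no section says so. Read literally, Table 2 pushes the rate down, as does reclassification after late treatment.

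A reader might also infer that unscheduled tissue is left unresolved. It is not: Section 7.1 makes those subjects non-responders. What is missing there is only a date limit.

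Finally, the narrowest route, Reading C, has little effect. That is correct, and the size of the problem should not be quoted from Reading A alone.

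**Conclusion.** The point holds as a contradiction within the protocol on its single formal test. Section 8.5.1 admits data that the objective, the endpoint and the separate Week 64 endpoints exclude, and nothing says which result counts.

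Neither the direction nor the size of bias can be fixed from the documents. At n = 24 with 8 responders needed:

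- **Override reading:** the false-positive rate is 7% to 52% for 5% to 20% conversion, and 18% at 10%.
- **Any-evidence reading:** power is 0.68 to 0.35 for 10% to 30% recurrence.
- **Missing-tissue reading:** the false-positive rate is about 2% to 6%.

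Each range rests on assumed rates. The same data could pass or fail depending on an unstated choice, which is reason enough to correct the rule before the primary analysis.

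**What to change.** Replace the time-frame sentence in Section 8.5.1 with a paragraph that states:

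1. The Week 36 frame runs from 14 days before to 14 days after Week 36, matching the immunology rule, or to a somewhat later bound that still ends before any fourth dose.
2. The Week 36 tissue collected in that frame determines response.
3. Only curative non-study treatment given up to that sample counts against the Week 36 endpoint.
4. The Section 7.1 classification of unscheduled biopsies is kept for this endpoint, limited to those taken up to that sample.
5. mITT subjects with no tissue in the frame count as non-responders. Section 8.5.8, which bars imputation beyond adverse-event dates, should refer to this rule.
6. The Week 64 and Week 88 frames are closed in the same way and do not overlap. With 14 days each side they are days 434–462 and 602–630.

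The cost is one paragraph and a cross-reference, with no change to procedures, dosing or sample size. A few very late samples would no longer give a Week 36 result. Item 5 also has a price in power: if 10% of subjects lack tissue, the alternative becomes 0.9 × 0.40 = 0.36 and power at n = 24 is 0.68 rather than 0.81, so Section 8.6 should say which figure applies.
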